8.1.3 Adverse Event Reporting Period

The adverse event reporting period for this trial begins when the patient receives the first treatment and ends 3 months after completion or withdrawl from the study. All adverse events that occur in trial subjects during the adverse event reporting period specified in the protocol will be reported, whether or not the even is considered treatment related.

The PI will follow adverse events with start dates occurring any time after informed consent is obtained until 7 (for non-serious AEs) or 30 days (for SAEs) after the last day of study participation. At each study visit, the investigator (or designee) will inquire about the occurrence of AE/SAEs since the last visit. Events will be followed for outcome information until resolution or stabilization.

8.1.4 Preexisting Condition

A preexisting condition is one that is present at the start of the study. A preexisting condition should be recorded as an adverse event if the frequency, intensity, or the character of the condition worsens during the study period.

8.1.5 General Physical Examination Findings

At screening, any clinically significant abnormality should be recorded as a preexisting condition. At the end of the study, any new clinically significant findings/abnormalities that meet the definition of an adverse event must also be recorded and documented as an adverse event.

8.1.6 Post-study Adverse Event

All unresolved adverse events should be followed by the investigator until the events are resolved to grade 1 or less, or become chronic, the subject is lost to follow-up, or the adverse event is otherwise explained. At the last scheduled visit, the investigator should instruct each subject to report any subsequent event(s) that the subject, or the subject's personal physician, believes might reasonably be related to participation in this study. The investigator should notify the study sponsor of any death or adverse event occurring at any time after a subject has discontinued or terminated study participation that may reasonably be related to this study. The sponsor should also be notified if the investigator should

become aware of the development of cancer or of a congenital anomaly in a subsequently conceived offspring of a subject that has participated in this study.

8.1.7 Abnormal Laboratory Values

A clinical laboratory abnormality should be documented as an adverse event if any one of the following conditions is met:

- Grade 3 or 4 lab abnormality other than what is otherwise explained elsewhere in the protocol
- The abnormality is of a degree that requires active management; e.g. change
 of dose, discontinuation of the drug, more frequent follow-up assessments,
 further diagnostic investigation, etc.

8.1.8 Hospitalization, Prolonged Hospitalization or Surgery

Any adverse event that results in hospitalization or prolonged hospitalization should be documented and reported as a serious adverse event unless specifically instructed otherwise in this protocol. Any condition responsible for surgery should be documented as an adverse event if the condition meets the criteria for and adverse event.

Neither the condition, hospitalization, prolonged hospitalization, nor surgery are reported as an adverse event in the following circumstances:

- Hospitalization or prolonged hospitalization for diagnostic or elective surgical procedures for a preexisting condition. Surgery should *not* be reported as an outcome of an adverse event if the purpose of the surgery was elective or diagnostic and the outcome was uneventful.
- Hospitalization or prolonged hospitalization required to allow efficacy measurement for the study.
- Hospitalization or prolonged hospitalization for therapy of the target disease of the study, unless it is a worsening or increase in frequency of hospital admissions as judged by the clinical investigator.

8.2 Recording of Adverse Events

The following subsections detail what information must be documented for each adverse event occurring during the time period specified.

Relationship to Study Intervention

The relationship to study intervention or study participation must be assessed and documented for all adverse events. Evaluation of relatedness must consider etiologies such as natural history of the underlying disease, concurrent illness, concomitant therapy, study-related procedures, accidents, and other external factors.

The following guidelines are used to assess relationship of an event to study intervention:

- 1. Related (Possible, Probable, Definite)
 - a. The event is known to occur with the study intervention.

- b. There is a temporal relationship between the intervention and event onset.
- c. The event abates when the intervention is discontinued.
- d. The event reappears upon a re-challenge with the intervention.

2. Not Related (Unlikely, Not Related)

- a. There is no temporal relationship between the intervention and event onset.
- b. An alternate etiology has been established.

Expectedness

The PI is responsible for determining whether an AE is expected or unexpected. An AE will be considered unexpected if the nature, severity, or frequency of the event is not consistent with the risk information previously described for the intervention. Risk information to assess expectedness can be obtained from preclinical studies, the investigator's brochure, published medical literature, the protocol, or the informed consent document.

Severity of Event

Adverse events will be graded for severity according to the Common Terminology Criteria for Adverse Events (CTCAE) version 4.0.

Intervention

Any intervention implemented to treat the adverse event must be documented for all adverse events.

At each contact with the subject, the investigator must seek information on adverse events by specific questioning and, as appropriate, by examination. Information on all adverse events should be recorded immediately in the source document, and also in the appropriate adverse event module of the case report form (CRF). All clearly related signs, symptoms, and abnormal diagnostic procedures results should be recorded in the source document, though should be grouped under one diagnosis.

The clinical course of each event should be followed until resolution to grade 1 or less, stabilization, becoming chronic, or until it has been determined that the study treatment or participation is not the cause. Serious adverse events that are still ongoing at the end of the study period must be followed up to determine the final outcome. Any serious adverse event that occurs after the study period and is considered to be possibly related to the study treatment or study participation should be recorded and reported immediately.

See form in appendix OHR-10 for recording of these events.

8.3 Reporting of Adverse Events

Any adverse events that is associated with study treatment and that is both serious and unexpected will be reported to the FDA by telephone, email, or fax within 7 days. All of the

investigators and the Thomas Jefferson University IRB will be notified as well. A follow-up safety report will be submitted within 15 days of initial notification.

In addition, Bristol-Myers Squibb will be notified within 24 hours of becoming aware of any serious adverse event.

8.4 Events of Special Interest

Adverse events of special interest are events of scientific and medical interest specific to the further understanding of the safety profile of this treatment and require close monitoring and rapid identification as there is specific guidelines for management of these toxicities. Notably, immune related adverse events, including Grade 4 hepatitis. Please see list of side effects and Immune-Related Adverse Event Guidance section and appendix 3 to further classify these events and subsequent management.

8.5 Data and Safety Monitoring Plan

All AEs and SAEs, safety and toxicity data, and any corrective actions will be submitted to the DSMC per the frequency described in the SKCC DSMP. The report to the SKCC DSMC will also include any unanticipated problems that in the opinion of the PI should be reported to the DSMC.

It is the responsibility of the Principal Investigator to oversee the safety of the study at his/her site. This safety monitoring will include careful assessment and appropriate reporting of adverse events as noted above, as well as the compliance and implementation of the Sidney Kimmel Cancer Center at Jefferson (SKCC) data and safety-monitoring plan. Medical monitoring will include a regular assessment of the number and type of serious adverse events by both the assigned Medical Monitor and the KCC DSMC.

8.5.1 Medical Monitoring and AE/SAE Reporting

Study site will reconcile the clinical database SAE cases transmitted to BMS Global Pharmacovigilance([contact]).

BMS GPV&E will email, upon request from the Investigator, the GPV&E reconciliation report. Requests for reconciliation should be sent to [contact].

SAEs, whether related or not related to study drug, and pregnancies must be reported to BMS within 24 hours. SAEs must be recorded on BMS or an approved form; pregnancies must be reported on a Pregnancy Surveillance Form.

SAE Email Address: [contact]

SAE [contact]

8.5.2 Data and Safety Monitoring Committee

A Medical Monitor is assigned to this study at the Thomas Jefferson University. This is a physician/pharmacist who is not directly involved in the trial, and is not currently collaborating with the sponsor/investigator on any other trial. The role of the Medical Monitor is to review all reportable AEs/SAEs (in real-time) including grading, toxicity assignments, non-reportable AEs (quarterly), protocol violations/deviations, as well as all other safety data and activity data observed in the ongoing clinical trial occurring at) Thomas Jefferson University. The

Medical Monitor may recommend reporting of adverse events and relevant safety data, and may also recommend suspension or termination of the study to the DSMC and TJU IRB.

Every KCC investigator initiated protocol includes requirements for reporting of adverse events based on CTC 4.0. All events are reported to the IRB and Medical Monitor using a password protected web-site. In addition all unexpected and serious adverse events (SAEs) are reported to the TJU IRB and to the Food and Drug Administration (FDA) if applicable. The investigator is required to submit all unexpected and serious adverse events to the TJU IRB and the Medical Monitor within the timeframes outlined in the below table. All AE/SAEs will be reported to the DSMC at the quarterly DSMC review meetings; however, if the Medical Monitor determines corrective action is necessary, an "ad hoc" DSMC meeting will be called. *Fatal adverse events related to treatment which are unexpected must be reported within 24 hours to the TJU IRB and the DSMC.*Fatalities not related to the study drug/device must be reported within 5 days. A summary of the reporting requirements for KCC investigator initiated Phase I and Phase II studies are presented below.

For expedited reporting requirements, see table below:

DSMC AE/SAE Reporting Requirements

	Grade 1	Grade 2	Grade 2	Gra	de 3	Gra	de 3	Grades 4
								and 5
	Unexpected	Unexpected	Expected	Unexpected	Unexpected	Expected with	Expected	Unexpected
	and			with	without	Hospitalization	without	and
	Expected			Hospitalization	Hospitalization		Hospitalization	Expected
Unrelated	Reviewed at	Reviewed at	Reviewed	5 Working	Reviewed at	5 Working	Reviewed at	Phase 1 -
Unlikely	Quarterly	Quarterly	at	Days	Quarterly	Days	Quarterly	48 Hours
	DSMC	DSMC	Quarterly		DSMC Meeting		DSMC Meeting	(Death: 24
	Meeting and	Meeting and	DSMC		and IRB		and IRB	Hours)
	IRB Annual	IRB Annual	Meeting		Annual Review		Annual Review	
	Review	Review	and IRB					Phase 2 -
			Annual					5 Working
			Review					Days
Possible	Reviewed at	5 working	Reviewed	48 Hours	Phase 1 -	48 Hours	Reviewed at	Phase 1 and
Probable	Quarterly	days	at	(Death: 24	48 Hours	(Death: 24	Quarterly	Phase 2 -
Definite	DSMC		Quarterly	Hours)		Hours)	DSMC Meeting	48 Hours
Bonnico	Meeting and		DSMC		Phase 2 -		and IRB	(Death: 24
	IRB Annual		Meeting		5 Working		Annual Review	Hours)
	Review		and IRB		Days			
			Annual					
			Review					

^{**}NOTE: This table is based on the NCI AE/SAE reporting Guidelines and the TJU IRB Policy and Procedures. Please follow the individual protocol AE/SAE reporting guidelines if more stringent reporting procedures are specified.

8.6 Unanticipated Problems

All incidents or events that meet criteria for unanticipated problems (UAPs) require the creation and completion of an unanticipated problem report form (OHR-20).

UAPs that pose risk to participants or others, and that are not AEs, will be submitted to the IRB on an OHR-20 form via the eazUP system within 10 working days of the investigator becoming aware of the event.

UAPs that do not pose risk to participants or others will be submitted to the IRB at the next continuing review.

8.7 Adverse Events

Grade 1 AEs will be reported to the IRB at continuing review.

Grade 2 AEs will be reported to the IRB at the time of continuing review.

8.8 Serious Adverse Events

SAEs will be reported to the IRB on OHR-10 forms via the electronic reporting system (eSAEy) according to the required time frames described below.

Grade 3-4 AEs that are unexpected and deemed to be at least possibly related to the study will be reported to the IRB within 2 working days of knowledge of the event.

Grade 3-4 AEs that are deemed unrelated to the study will be reported to the IRB within 5 working days.

Grade 5 AEs will be reported to the IRB within one working day of knowledge of the event.

All SAEs will be submitted to the IRB at continuing review, including those that were reported previously.

9.0 EVALUATION OF RESPONSE

9.1 Evaluation of Clinical Response

Patients who receive at least one IEMBO treatment will be evaluable for clinical response, including survival. Patients who were not treated with IEMBO due to technical problems will not be included for evaluation of clinical response. Patients will first be evaluated with scans between Cycles 2 and 3 to insure no evidence of rapid progression. Initial radiographic response will be determined following four IEMBO treatments if both. Patients with SD, PR, or CR at this time will have repeat scans after every two treatment cycles.

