3.3 Secondary Study Endpoints

- 1. All toxicities using the NCI CTCAE Version 4.0.
- 2. Progression Free Survival (hepatic and systemic PFS)
- 3. Overall survival

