5.3 Procedure of Immunoembolization

5.3.1 Hospital Admission

Patients will be admitted to Thomas Jefferson University Hospital and undergo immunoembolization on Day #2, following IPI + NIVO on Day #1.

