5.3.2 Access of the hepatic artery

An angiogram of the hepatic arteries will be obtained by the established technique. Non-ionized contrast will be used for angiographic studies to minimize the risk for allergic reactions. One of the hepatic lobes will then be treated based on the locations and sizes of the tumors. The proper arterial catheter placement, appropriate perfusion pattern to targeted tumors and existence of arteriovenous shunting that may cause pulmonary embolism by ethiodized oil will be thoroughly evaluated by angiography prior to the

embolization procedure. Such a degree of shunting is rarely ever seen in this patient population but discretion of the interventional radiologist will be used if shunting identified.

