7.2.1 Analysis Population

The evaluable population includes all subjects enrolled who receive at least four combination treatments (IPI + NIVO + IEMBO at initial every 3 week intervals or NIVO + IEMBO if IPI dropped due to toxicity and IEMBO alone if NIVO dropped due to toxicity) and complete assessment after four treatments.

The As-treated population includes all subjects who receive any treatment and will be used to evaluate baseline characteristics as well as all secondary endpoints for safety and efficacy as the collected data allows.

7.2.2 Primary Endpoint:

The primary endpoint is the best hepatic response (CR + PR + SD) by response criteria (RECIST 1.1) after four combination treatments. The estimate of the hepatic metastasis stabilization rate will be presented with corresponding 95% confidence intervals. The method of Atkinson and Brown will be used to adjust for the two-stage design.

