7.2.3 Secondary and Exploratory (Correlative) Endpoints

- 1. All toxicities using the NCI CTCAE Version4.0.
- 2. PFS (hepatic and systemic PFS)
- 3. Overall survival
- 4. Systemic and local immune/inflammatory response correlatives
 - a. Degree and classification of tumor-infiltrating cells
 - b. Presence and changes in PD-L1 expression in tumor and tumor-infiltrating cells
 - c. Changes in immune tumor microenvironment (immune gene signature)
 - d. Tumor mutational burden prior to treatment
 - e. Changes in TCR repertoire analysis (ImmunoSeq)
 - f. Changes in cytokine levels (multiplex cytokine measurements)
 - g. Changes in PBMC cell populations, including T cells and MDS.

The PFS and OS will be estimated using the Kaplan-Meier method. The toxicity rates will be estimated with corresponding 95% confidence intervals. Correlative endpoints including repeated measures of cytokine and molecular marker levels in tissue or serum will be analyzed using appropriate linear mixed effects models.

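### Sections 9.1 and 7.2.1 define different populations for overall survival (and, by fair reading, PFS): a patient given ipilimumab and nivolumab but never embolized is counted under one and not the other

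*Combined protocol and SAP*

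**What the plan says.** Section 7.2.1 (Analysis Population) defines two sets. The evaluable population needs at least four treatments and the assessment that follows them. The second set is wider: "The As-treated population includes all subjects who receive any treatment and will be used to evaluate baseline characteristics as well as all secondary endpoints". The sentence ends with a qualifier, "all secondary endpoints for safety and efficacy as the collected data allows".

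PFS and OS are the secondary efficacy endpoints (3.3 and 7.2.3). Section 7.2.3 gives the estimator, "The PFS and OS will be estimated using the Kaplan-Meier method", and names no population.

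Section 9.1 (Evaluation of Clinical Response) sets its own rule: "Patients who receive at least one IEMBO treatment will be evaluable for clinical response, including survival". Its next sentence is the exclusion: "Patients who were not treated with IEMBO due to technical problems will not be included for evaluation of clinical response".

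On sequence, section 5.3.1 has patients "undergo immunoembolization on Day #2, following IPI + NIVO on Day #1". Under 5.3.2, angiography just before embolization checks catheter position, perfusion and shunting, and "discretion of the interventional radiologist will be used if shunting identified". Sections 9.6 and 9.7 start the PFS and OS clocks at the start of treatment.

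**The concern.** Two sections give different answers to the question of who is in the OS analysis. The 9.1 answer depends on whether embolization was achieved, which is learned after Day 1 drug has been given and the clock has started. A time-to-event estimate restricted in this way no longer describes everyone who started the regimen. It also drops from view the patients in whom the planned IEMBO could not be delivered. In a single-arm trial no control group is subject to the same selection.

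At stake is the interpretation of the secondary PFS and OS estimates. If the contradiction stays, the survival denominator is left to be settled at reporting.

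**Working it through.** The contradiction is settled by comparing the text. Arithmetic serves only to show how much it could matter.

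**1. Can a patient fall between the two sets?**

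- Exclusion criteria (4.2): no angiographic criterion.
- Screening work-up (6.1.1 and schedule 15.1): no angiogram listed.
- Day 1: ipilimumab and nivolumab (5.3.1, 5.4).
- Day 2: angiogram, then IEMBO if feasible (5.3.1, 5.3.2).

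Feasibility may therefore first be tested after study drug has been given. A patient treated on Day 1 and never embolized is classified as follows:

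| Rule | Counted for OS? | Counted for PFS? |
|---|---|---|
| 7.2.1, As-treated | Yes | Yes |
| 9.1 | No; survival is named | No, by fair reading; PFS is defined in the same chapter (9.6) but not named in 9.1 |

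**2. Is the primary design affected?** The plan's own figures were reproduced by exact two-stage binomial calculation: stop at 8 or fewer of 13, reject at 26 or more of 35.

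P(reject | p) = Σ over x₁ = 9 to 13 of b(13, x₁, p) × P(X₂ ≥ 26 − x₁), with X₂ ~ Bin(22, p)

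- p = 0.60: type I error 0.0499 (plan: 0.05); early stopping 0.647 (plan: 0.65).
- p = 0.80: power 0.808, so type II error 0.192 (plan: 19%).

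These figures belong to the primary endpoint. Every treatment pattern that 7.2.1 accepts for the evaluable population includes IEMBO, so a never-embolized patient is outside it under either rule.

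**3. How far could a survival proportion move?** The plan states no PFS or OS figure and no technical-failure rate, so all inputs here are assumed: N = 35 treated, E = 24 event-free at some time point with no earlier censoring (the Kaplan-Meier estimate is then the simple proportion), and k never embolized, of whom e are event-free.

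- As-treated: E/N = 24/35 = 68.6%.
- Under 9.1: (E − e)/(N − k).
- Difference: k/(N − k) × (E/N − e/k).

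| k | All excluded had events (e = 0) | None had events (e = k) |
|---|---|---|
| 2 | 24/33 = 72.7% (+4.2 points) | 22/33 = 66.7% (−1.9 points) |
| 3 | 24/32 = 75.0% (+6.4 points) | 21/32 = 65.6% (−2.9 points) |

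The difference formula gives zero when the excluded patients do as well as the rest (e/k = E/N), and nothing changes when k = 0.

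**4. If such patients are replaced.** Section 4.3.3 replaces subjects withdrawn before the fourth-cycle assessment for reasons other than deterioration or toxicity. If that applies, 35 embolized patients sit inside an As-treated set of 37 or 38. With 24 of the 35 embolized patients event-free (68.6% under 9.1), the As-treated figure is 24/37 = 64.9% or 24/38 = 63.2% if all the replaced patients had events. It is 26/37 = 70.3% or 27/38 = 71.1% if none did. The gap has the same order of size and can again go either way.

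**The case against.** The strongest reply is that 7.2.1 is the dedicated population section of the statistical plan and is explicit for secondary endpoints, so it should be taken to govern, with 9.1 read as loose wording. Sections 4.3.2 and 6.1.7 point the same way: they require survival follow-up of all subjects, and follow-up for progression and survival of all patients. This is the sensible reading, but no section states it, and 9.1 names survival expressly. The follow-up rules also mean that the data should exist, so the 7.2.1 qualifier about data availability does not justify leaving these patients out.

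Other parts of the reply stand:

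- The exclusion sentence taken alone speaks only of clinical response. Survival enters through the sentence before it, and PFS is covered by inference.
- Few patients should be affected. Section 5.3.2 describes significant shunting as very uncommon in this population, 5.3.3 adapts the procedure to variant anatomy, and a patient embolized later meets the 9.1 rule.
- PFS and OS are descriptive, with no test or threshold.

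A reader might infer that the rule favours the combination. The documents do not support a direction: nothing in them links anatomy or shunting to prognosis, and the range above spans zero. A reader might also infer that the sponsor picked the denominator after seeing results. The rule is written in advance; only a patient's membership depends on a later event. The revision history records a clarification of 9.1 evaluability in Version 6, which is not evidence of a data-driven choice.

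**Conclusion.** Wrong as written, as an internal contradiction of minor severity. Sections 9.1 and 7.2.1 give different populations for OS, and by fair reading for PFS, and the 9.1 population is conditioned on an event after time zero. The estimates can be biased in either direction, upward if the excluded patients do worse than the rest.

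In the assumed case without replacement, the shift for 2 or 3 never-embolized patients runs from about −2.9 to +6.4 percentage points. That range rests on an invented event-free count and an invented number of technical failures. The true number affected is probably small and may be zero. It would be wrong to read this as a threat to the trial's main conclusion: the primary endpoint, the stopping rule and the sample size do not change.

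**What to change.** Amend 9.1 to state that PFS and OS use the As-treated population of 7.2.1, including patients who receive ipilimumab and nivolumab but no IEMBO, and name that population in 7.2.3. Keep the subset with at least one IEMBO as a sensitivity analysis only, reported with the number excluded and the reason for each.

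The cost is wording. Sample size, treatment and data collection stay as they are, because follow-up of these patients is already required. The reported estimates may come out slightly lower or higher than under 9.1.
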